### 1. PROTOCOL SUMMARY

#### 1.1 SYNOPSIS

PROTOCOL TITLE: STUDY TO EVALUATE AND EXPLORE SCALES FOR

REPETITIVE AND RESTRICTED BEHAVIORS AND DIGITAL

BIOMARKERS IN CHILDREN, ADOLESCENTS AND ADULTS WITH AUTISM SPECTRUM DISORDER (ASD)

SHORT TITLE Evaluation of scales for repetitive and restricted behaviors,

digital biomarkers in children, adolescents and adults with ASD

PROTOCOL NUMBER: BP40331

VERSION: 2

TEST PRODUCT: NA

PHASE:

#### RATIONALE

Autism Spectrum Disorder (ASD) is a neurodevelopmental condition characterized by persistent deficits in social communication and social interaction and presence of repetitive patterns of behaviors, interests, or activities. In addition to these core deficits, individuals with ASD may suffer from a range of co-morbid conditions and associated behavioral problems, including irritability, depression or anxiety, attention deficits, obsessive compulsive symptoms, seizures and sleep disruption. Restricted and repetitive behaviors (RRBs) are core diagnostic features of ASD according to the Diagnostic and Statistical Manual of Mental Disorders (DSM-5). The prevalence of ASD is between 1 in 45 to 1 in 68 children. The etiology of ASD is highly genetic although environmental factors also contribute. Heritability estimates from family and twin studies suggest that about 90% of variance can be attributed to genetic factors, making ASD the neuropsychiatric disorder most affected by genetic factors. At present, no pharmacological treatment has been approved by Health Authorities to treat the core deficits of ASD, and currently available approved drugs in the US only (risperidone and aripiprazole) address only associated behavioral problems (used for the treatment of irritability associated with ASD). Nonpharmacological treatments have been developed to address the core symptoms; however, clear efficacy has been difficult to demonstrate in large controlled clinical trials and they are time consuming and costly. Accordingly, there is a high unmet medical need for pharmacological treatments of these core symptoms of the disorder.

RRBs constitute a broad range of behaviors, including simple motor stereotypies as well as more complex ritualized and rigid behaviors, compulsions, and restricted interests that vary in frequency, intensity, and duration. Although there is an extensive literature on RRBs in subjects with ASD, the instruments available and widely used to assess these behaviors in clinical trials are not fully understood or have limitations to assess change in these behaviors, in particular in clinical trials. BP40331 is a non-drug study which seeks to characterize different scales to measure repetitive and restricted behaviors in different ASD sub-populations over time and also to explore the use of digital biomarkers. The results from this study will inform the planning and setup of subsequent drug interventional studies in programs aimed to treating restrictive and repetitive behaviors in ASD.

#### **OBJECTIVES AND ENDPOINTS**

#### **Primary Objectives**

 To characterize and compare the psychometric properties of different scales for RRB in individuals with ASD.

#### **Secondary Objectives**

- To evaluate the effect of Age and intelligence quotient (IQ) on RRB in participants with ASD.
- To evaluate correlations between scales.
- To explore the factor structure within each scale.

Endpoints
Days on which participants collect data using the smartphone and wearable.

 
Daily participant/caregiver-reported outcome ratings of RRBs and social interaction.
 

Frequency of repetitive movements.

 
Frequency of locations visited around the home and beyond.
 

 
Relationship between anxiety and heart rate.
 

 
Accuracy and speed of emotion recognition.
 

 
Spatial working memory capacity.
 

 
Speech properties (pitch, volume, shimmer, jitter).
 

 
Conversational patterns (duration of speech, turn-taking).
 

#### **OVERALL DESIGN**

Each participant with ASD will be evaluated using several scales and tests at each visit at the clinic. There will be four clinic visits in total (screening period included). Table 1 provides an overview of scales and tests to be used in the study. In addition, digital biomarker data will be collected from all participants. *Typically developing (TD)* healthy participants will be enrolled for validation of digital biomarkers only.

Table 4 Overview Clinical Scales/Clinical Outcome Assessments

Scale group	Specific scale	Completed by	Children	Adolescents	Adults	Time [min]	
SB5 abbrev. Stanford- Binet		clinician	mandatory	mandatory	mandatory	15-20	
ADOS-2		clinician	mandatory	mandatory	mandatory	40-60	
CGI-I+CGI-S		clinician	mandatory	mandatory	mandatory	5+5	
CY-BOCS-ASD	)	clinician	mandatory	mandatory	mandatory	~ 20	
MERS-R		clinician	mandatory	mandatory	mandatory	15-20	
RBS-R		caregiver	mandatory	mandatory	mandatory		
RBQ-2 	RBQ-2 for Children	caregiver	mandatory	mandatory	if deemed appropriate  by Investigator	20-30	
	RBQ-2A for adults	participant- reported		if deemed appropriate  by Investigator based on mental age	mandatory	20-30	
Routine Inventory 	CRI-R for Children	caregiver	mandatory	mandatory	if deemed appropriate by Investigator	~ 17	
	ARI for adults	participant- reported		if deemed appropriate  by Investigator based on mental age	mandatory	~ 17	
BRIEF	BRIEF for Children	caregiver	mandatory	mandatory		10-15	
	BRIEF-A for Adults	caregiver			mandatory	10-15	
Vineland™-II (survey)		clinician	mandatory	mandatory	mandatory	45-60	
	Family Impact Scale	caregiver	mandatory	mandatory	mandatory	~ 5	
PedsQL	Generic Core & Cognitive Function ing Scales	participant- reported	mandatory	mandatory	mandatory	~10	

Table 4 Overview Clinical Scales/Clinical Outcome Assessments (cont.)

SSP	Short Sensory profile	caregiver	mandatory	mandatory	-	5-15
Sleep 	CSHQ	caregiver	mandatory	mandatory	if deemed appropriate  by Investigator	5-10
	PSQI	participant- reported		if deemed appropriate  by Investigator	mandatory	~ 5
RMET 	RMET-C for Children	participant- reported	if deemed appropriate  by Investigator	if deemed appropriate  by Investigator.	if deemed appropriate  by Investigator	~ 20
	RMET-R for adults	participant- reported		if deemed appropriate  by Investigator.	if deemed appropriate  by Investigator	~ 20
Anxiety 	HAM-A	clinician			mandatory	10-15
	PRAS- ASD	caregiver	mandatory	mandatory		~ 10
	BAI	participant- reported		if deemed appropriate  by Investigator	mandatory	5

1. For scales where a pediatric and an adult scale or scale version exists, both versions should be administered in adolescents and adults, if deemed appropriate by Investigator. For further details see protocol Section 8.1.1.3. In any case at least one scale / scale version will be mandatory.

#### Length of Study

The total duration of the study (from screening through to study completion) for each participant will be approximately 15 weeks divided as follows:

- Screening and run-in period: up to 4 weeks.
- Study period: 12 weeks.

#### **End of Study**

The end of the study is defined as the date when the last participant last observation (LPLO) occurs. LPLO is expected to occur approximately 12 weeks after the last participant had the Baseline visit.

#### PARTICIPANT POPULATION

The participants are children age 5 to 12 years, adolescents age 13 to 17 years, and adults age 18 to 45 years who meet all diagnostic criteria of ASD according to the DSM-5 criteria.

In addition,  $45\ TD$  healthy participants (15 children age 5 to 12 years,  $15\ adolescents\ age\ 13\ to\ 17$  years, and  $15\ adults\ age\ 18\ to\ 45\ years$ ) will be enrolled for validation of digital biomarkers only.

2. For the RMET, either the pediatric or adult version should be administered. If none of the two RMET versions is deemed appropriate for the participant the RMET can be skipped.

#### INCLUSION/EXCLUSION CRITERIA

#### **INCLUSION CRITERIA**

Participants with ASD and TD healthy participants are eligible to be included in the study only if all of the following criteria apply:

#### Inclusion criteria specific to typically developing healthy participants:

1. Male and female TD healthy participants age 5 to 45 years inclusive.

## Inclusion criteria specific to typically developing healthy participants and participants with ASD:

- Able and willing to provide written informed consent or assent, as per local requirements
  according to International Council for Harmonisation (ICH) and local regulations.
   Alternatively, a legally authorized representative must be able to consent for the participant
  according to ICH and local regulations and assent must be given whenever possible.
- 3. Availability of a parent or other reliable caregiver who is fluent in English and has frequent and sufficient contact with the participant. The same person must agree to accompany the participant to all clinic visits and provide information about the participant's behavior and symptoms and must agree to oversee the participant's adherence with protocol-specified procedures.
- In the Investigator's opinion, the participant must be able to participate and is deemed
  appropriate for participation in the study, capable of following the study schedule of
  assessments.
- 5. English proficiency compatible with the study measurements as judged by the Investigator.
- 6. Hearing, vision, *and speech* compatible with the study measurements as judged by the Investigator.

#### Inclusion criteria specific to participants with ASD:

- 7. Male and female participants with ASD 5 to 45 years inclusive.
- Abbreviated Battery Intelligence Quotient (ABIQ) ≥ 50 as assessed by Stanford-Binet Intelligence Scales fifth Edition (SB5) at screening or within the last 12 months prior to screening.
- ASD diagnosis by DSM-5 criteria by a qualified clinician.
- 10. The ASD diagnosis confirmed by Autism Diagnostic Observation Schedule (ADOS-2) done by a certified rater at screening, or within the last 6 months prior to screening.
- 11. Children's Yale-Brown Obsessive Compulsive Scale modified for ASD (CY-BOCS-ASD) total score of at least 12.
- 12. Clinical Global Impression–Severity (CGI-S) scale ≥ 4 (moderately ill) at screening about participant's current autism severity.
- 13. Medications should be stable for 4 weeks (6 weeks for Fluoxetine) and behavioral interventions for 6 weeks prior to screening. Investigator expects stability of these treatments for the duration of the study.

#### **EXCLUSION CRITERIA**

Participants with ASD and TD healthy participants are excluded from the study if any of the following criteria apply:

#### Exclusion criteria specific to typically developing healthy participants:

1. Typically developing healthy participants with first degree relative with ASD.

## Exclusion criteria specific to typically developing healthy participants and participants with ASD:

- Participation in an investigational drug or device study within 4 weeks, or five times the
  half-life (if it is a drug study) of the investigational molecule (whichever is longer), prior to
  screening and the participant is expected not to enroll in any other trial during the study.
- Co-occurring disease or condition that could interfere with, or treatment which might interfere
  with, the conduct of the study, or that would, in the opinion of the Investigator, pose an
  unacceptable risk to the participant in this study.
- 4. Unstable or uncontrolled clinically significant psychiatric and/ or neurological disorder that may interfere with the objectives of the study.

#### Exclusion criteria specific to participants with ASD:

- 5. Participants with known "syndromic" ASD (e.g., Fragile-X syndrome, Angelman Syndrome, Prader-Willi, Rett's syndrome, tuberous sclerosis, Dup15q syndrome).
- 6. History of alcohol misuse and/or illicit drug use during the last 12 months prior to screening.

#### NUMBER OF PARTICIPANTS

Approximately 90 participants with ASD will be enrolled into six cohorts with approximately 15 participants each. The six cohorts are defined by all combinations of the below categories for the two factors ABIQ and age:

- ABIQ: participants with ABIQ ≥ 70 vs participants with ABIQ ≥ 50 and < 70.

- Age: children 5 to 12 years; adolescents 13 to 17 years and adults 18 to 45 years.

In addition, 45 TD healthy participants (15 children age 5 to 12 years, 15 adolescents age 13 to 17 years, and 15 adults age 18 to 45 years) will be enrolled for validation of digital biomarkers only.

#### **CONCOMITANT MEDICATIONS**

Any stable medication (including over-the-counter [OTC] or prescription medicines, approved dietary and herbal supplements, nutritional supplements) at screening should remain stable throughout the study. However, dose changes due to adjustments for change in body weight/ age and or triggered by therapeutic monitoring will be allowed. Other changes in prescribed medication need to be approved by the Sponsor (Medical Monitor or designee).

#### Non-Pharmacological Interventions

Non-pharmacological interventions (e.g., subject psychotherapy, cognitive behavioral therapy, applied behavioral analysis (ABA), speech therapy, occupational therapy, rehabilitative therapy, and social skills training) must be stable for 4 weeks prior to screening and must remain stable throughout the ongoing study in terms of type of intervention and intensity. Minor changes in ongoing treatment (e.g., missed therapy sessions due to holiday/vacation; planned break in therapy due to school holidays; changes in college/school programs) are not considered significant and need not to be discussed with the Sponsor (Medical Monitor or designee).

A complete history of non-pharmacological interventions for the treatment of ASD including all previously completed therapies will be reported on eCRF.

## F. Hoffmann-La Roche Ltd

1.2	SCHEDULE OF	ACTIVITIES
1.4	SCHEDULE OF	ACTIVITIES

The schedule of the activities is provided in Table 1 and Table 2.

Table 1 Schedule of Activities – Main table (ASD participants only)

	Screening	Baseline	Week 2	Week 5 Phone 	Week 8 Phone 	Week 12	Early With- drawal
Davis	Clinic visit 1	Clinic visit 1	Clinic visit 	Contact		Clinic visit 1	Clinic visit 1
Day	-21	1	15	36	57	85	NA
Time window (days)	+/- 7	NA	+/-2	+/-4	+/-4	+/-7	NA
Informed Consent	X						
Stanford Binet (SB-5) abbreviated IQ test 	X						
ADOS-2 	X						
CY-BOCS-ASD	х	Х	Х			Х	Х
CGI-S	х	Х	Х			Х	Х
CGI-I			X			Х	X
Incl/Excl criteria	×						
Demography	×						
Medical History (incl. psychiatry)	X						
MERS-R		Х	Х			Х	Х
RBS-R		Х	Х			Х	Х
RBQ-2 		Х	Х			Х	Х
CRI-R  / ARI 		Х	Х			Х	Х
BRIEF		Х	Х			Х	Х
Vineland ™ -II (survey)		Х				Х	Х
PedsQL (family impact scale)		Х	Х			Х	Х
PedsQL (core and cognitive scale)		Х	χ			Х	Х
SSP		Х	Х			Х	Х
CSHQ  / PSQI 		х	Х			Х	Х
HAM-A 6 / BAI 6 / PRAS-ASD 6		х	Х			Х	Х
RMET 		Х				Х	Х
Drug Acceptability Survey			Х				
Phone contacts 				Х	Х		
Previous & Concomitant Treatments	•						-
Adverse Events 7	•						-
Digital Biomarkers 	•						

- 1. Clinical visits can be performed over 2 days.
- 2. See Table 2 for collection of Digital Biomarker data from all participants.
- 3. Follow-up by telephone will include questions about participant's welfare.
- 4. A Stanford-Binet Intelligence scales test up to 12 month old is acceptable.
- 5. An ADOS-2 test up to 6 month old is acceptable.
- Age specific scales, and scales deemed appropriate by Investigator, will be completed for details (see Table 4).
- 7. Only adverse events and serious adverse events caused by a protocol-mandated intervention should be reported (see Section 8.3).

Table 2 Schedule of Activities for Collection of Digital Biomarkers.

All participants (typically developing healthy participants and participants with ASD)

	Screening Clinic visit 	Baseline Clinic visit 	Week 2 Clinic visit  Or  Phone Contact 	Week 5 Phone  Contact		Week 12 Clinic visit 1	Early With- drawal Clinic visit 
Day	-21	1	15	36	57	85	NA
Time window (days)	+/- 7	NA	+/-2	+/-4	+/-4	+/-7	NA
Informed Consent	Х						
Stanford Binet (SB-5) abbreviated IQ test 	Х						
Incl/Excl criteria	Х						
Demography	Х						
Identification of targeted behaviors for app	Х						
Hand over devices and training	Х						
dBM run-in to validate devices and apps	←						
RMET 		Х				Х	Х
Digital Biomarker Collection		-					
Phone contacts 			X β	Х	Х		
Return devices and satisfaction survey 5						Х	Х
Adverse Events 	-						-

Digital biomarkers will be collected from all participants, those with ASD and the *typically developing (TD)* healthy participants.

- 1. Clinical visits can be performed over 2 days.
- 2.A Stanford-Binet Intelligence scales test up to 12 month old is acceptable.
- 3. Follow-up by telephone will include questions about participant's welfare and progress in collection of digital biomarker data.
- 4. The RMET will provide anchor data for analysis of digital biomarkers and will be conducted also in *TD* healthy participants. An age specific version of the RMET will be completed as deemed appropriate by Investigator for details (see Table 4).
- 5. Final satisfaction surveys on the participant's experience about collection of digital biomarker will be completed by participants *and by caregivers*.
- 6. For all participants with ASD at week 2 a mandatory clinic visit will be completed. For the *TD* healthy participants at week 2 a telephone contact will be sufficient.
- 7. Only adverse events and serious adverse events caused by a protocol-mandated intervention should be reported see Section 8.3.

### 2. INTRODUCTION

Autism Spectrum Disorder (ASD) is a neurodevelopmental condition characterized by persistent deficits in social communication and social interaction and presence of repetitive patterns of behaviors, interests, or activities. The prevalence of ASD is between 1 in 45 to 1 in 68 children (Zablotsky et al 2015, Christensen et al 2016, Blumberg et al 2013). Core symptoms of ASD are usually observed by 3 years of age, although language development might delay identification of symptoms. Moreover, although initial symptoms may be identified between 12 and 24 months, typically this does not manifest as a formal diagnosis and even if a diagnosis is made, this may not be stable (Kleinman et al 2008; Chawarska et al 2009). Deficits in social interaction manifest themselves as impaired use of nonverbal communication, delayed and reduced interactions with peers, absent sharing of enjoyable experiences and interest with peers, and lack of social judgment. Abnormalities in communication may include a delay in verbal language development, impaired expressive language, deficient language pragmatics, as well as stereotyped, repetitive, or idiosyncratic use of language. Stereotyped and repetitive behavior manifests as a preoccupation with stereotyped or restricted interests, adherence to routines, rigidity, perseveration, motor mannerisms, and preoccupation or fascination with parts of items and unusual visual exploration. In addition to these core deficits, individuals with ASD may suffer from a range of comorbid conditions and associated behavioral problems, including irritability, depression or anxiety, attention deficits, obsessive compulsive symptoms, seizures and sleep disruption (Houghton et al 2017). The etiology of ASD is highly genetic although environmental factors also contribute. Heritability estimates from family and twin studies suggest that about 90% of variance can be attributed to genetic factors, making ASD the neuropsychiatric disorder most affected by genetic factors (Levy et al 2009).

At present, no pharmacological treatment has been approved by Health Authorities to treat the core deficits of ASD, and currently available approved drugs in the US only (risperidone and aripiprazole) address only associated behavioral problems (used for the treatment of irritability associated with ASD) (Wink et al 2010). Non-pharmacological treatments have been developed to address the core symptoms; however, clear efficacy has been difficult to demonstrate in large controlled clinical trials and they are time consuming and costly (Warren et al 2011). Accordingly, there is a high unmet medical need for pharmacological treatments of these core symptoms of the disorder.

#### 2.1 STUDY RATIONALE

Restricted and repetitive behaviors (RRBs) are core diagnostic features of ASD according to the Diagnostic and Statistical Manual of Mental Disorders (DSM-5). RRBs constitute a broad range of behaviors, including simple motor stereotypies as well as more complex ritualized and rigid behaviors, compulsions, and restricted interests that vary in frequency, intensity, and duration.

Factor analysis of RRBs have identified at least two groups of RRBs; one comprising repetitive sensory and motor behaviors (RSMB) also known as lower-order RRBs such as hand flapping and body rocking, and the other comprising more abstract behaviors also called insistence on sameness (IS) or "higher-order" RRBs, such as routines and circumscribed interests (Richler et al 2010). Although there is an extensive literature on RRBs in subjects with ASD, the instruments available and widely used to assess these behaviors in clinical trials are not fully understood or have limitations to assess change in these behaviors, in particular in clinical trials (Scahill et al 2015).

BP40331 is a non-drug study which seeks to characterize different scales to measure repetitive and restricted behaviors in different ASD sub-populations over time and also to explore the use of digital biomarkers. The results from this study will inform the planning and setup of subsequent drug interventional studies in programs aimed to treating restrictive and repetitive behaviors in ASD.

#### 2.2 BENEFIT/RISK ASSESSMENT

Participants are not expected to experience physical, psychological or social harm by participating in study BP40331. As no study treatment will be given and no invasive procedures will be performed in this study there are no risks associated with participation in this study. Digital biomarkers assessments using smartphone and other sensors are not expected to cause harm or major inconvenience to the participants.

There is no individual benefit for ASD participants in this study. However, the results of this study may help the evaluation in future Phase II studies in subjects with ASD, ensuring that the most optimal scales and tests will be used to demonstrate efficacy of new drugs to treat restrictive and repetitive behaviors in ASD. Data are not considered to be detrimental for caregivers and participants and individual results will be shared at the end of the study, if requested.

#### 3. OBJECTIVES AND ENDPOINTS

The objectives and corresponding endpoints are provided in Table 3.

Table 3 Objectives and Endpoints

#### **Primary Objectives**

 To characterize and compare the psychometric properties of different scales for RRB in individuals with ASD.

### **Secondary Objectives**

[figure not shown]
- To evaluate the effect of age and intelligence quotient (IQ) on RRB in participants with ASD
- To evaluate correlations between scales.
- To explore the factor structure within each scale.

	•		
	Tertiary/Exploratory Objectives		Endpoints
•	To assess participant adherence to remote monitoring with a smartphone application and wearable.	•	Days on which participants collect data using the smartphone and wearable.
•	To capture daily participant and/or caregiver reports of core ASD symptoms with smartphone application (app).	•	Daily participant/caregiver-reported outcome ratings of RRBs and social interaction.
•	To continuously and objectively measure ASD symptoms with wearable technology.	•	Frequency of repetitive movements.
		•	Frequency of locations visited around the home and beyond.
			Relationship between anxiety and heart rate.
•	To frequently measure social and cognitive performance with smartphone		Accuracy and speed of emotion recognition.
	арр.	•	Spatial working memory capacity.
			Speech properties (pitch, volume, shimmer, jitter).
		•	Conversational patterns (duration of speech, turn-taking).

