# 8.1.1.3 Administration of both the Caregiver and Participant-reported Scale Version "if deemed appropriate by Investigator"

For adolescents and adults both versions of the Routine Inventories and the Repetitive Behavior Questionnaires scale should be administered in individual participants at the same visit if the Investigator deems the non-mandatory version of the scale appropriate (see Table 4 and Sections 8.1.1.10 and 8.1.1.11). This includes the participant-reported adult versions (RBQ-2A and ARI) and the caregiver-completed pediatric versions (RBQ-2 and CRI-R).

- For adolescent participants the caregiver-completed RBQ-2 and CRI-R are mandatory scales. The participant-reported versions RBQ-2A and ARI will be completed as well, if deemed appropriate, and if the Investigator deems the participant able to complete these scales based on mental age.
- For adult participants the self-reported versions RBQ-2A and ARI are mandatory scales.
   The caregiver-reported RBQ-2 and CRI-R will be completed as well, if deemed appropriate by Investigator.

Similarly, and "if deemed appropriate by Investigator," the caregiver will complete the CSHQ for adult participants- Adolescent participants will complete the participant-reported PSQI and BAI (see Table 4).

If an adult participant is unable to complete a self-reported adult scale (e.g., because of mental age or other reasons) the corresponding caregiver-reported scale version will be used if it is deemed appropriate by Investigator and if such a scale version exists (i.e., RBQ-2 is to be completed if RBQ-2A is skipped, CRI-R if ARI is skipped, CSHQ if PSQI is skipped).

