### 8.1.1.20 Hamilton Anxiety Rating Scale (HAM-A)

The HAM-A is a clinician-rated scale to analyze the severity of symptoms of anxiety. The HAM-A consists of 14 items, each defined by a series of symptoms, and measures both psychic anxiety (mental agitation and psychological distress) and somatic anxiety (physical complaints related to anxiety). The scale is intended for adults, adolescents, and children (Hamilton et al 1959).

The HAM-A will be completed only for adult participants in this study. It will take the clinician-rater about 10-15 minutes to administer the HAM-A.

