# 9.2.4 Statistical methods for the Secondary Objectives

The effect of age and IQ on RRBs in subjects with ASD will be evaluated with graphical displays and by applying regression models with the RRB scale as dependent and age and IQ and other possible covariates

The correlation structure between scales will be evaluated by means of multivariate methods such as principal component analyses and factor analyses

All listed p-values will be interpreted only as descriptive weights and not in a confirmatory sense.

Further details of planned analyses will be provided in the technical document.

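### Does the single factor-analysis sentence in Section 9.2.4 leave the within-scale objective without a method and the between-scale analysis without usable data?

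*Combined protocol and SAP*

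**What the plan says.** Two of the three secondary objectives in Table 3 (Section 3) matter here: "To evaluate correlations between scales" and, as a separate item, "To explore the factor structure within each scale". The primary objective is "To characterize and compare the psychometric properties of different scales for RRB in individuals with ASD".

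Section 9.2.4 has one sentence on multivariate methods: "The correlation structure between scales will be evaluated by means of multivariate methods such as principal component analyses and factor analyses". The same section treats all p-values as descriptive and closes with "Further details of planned analyses will be provided in the technical document". That technical document is not among the documents supplied. The nearest within-scale method elsewhere in Section 9 is Cronbach's alpha, which Section 9.2.3 lists for the primary objective.

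Who completes which version is set in Table 4 and Section 8.1.1.3. For the paired repetitive-behaviour scales, "For adolescent participants the caregiver-completed RBQ-2 and CRI-R are mandatory scales" and "For adult participants the self-reported versions RBQ-2A and ARI are mandatory scales". Section 8.1.1.3 adds that adolescents and adults should have the other version as well, at the same visit, where the investigator finds it appropriate. In Table 4, RBQ-2 and CRI-R are also mandatory for children, who never receive RBQ-2A or ARI. A few other scales are strictly split by age. For example, "The HAM-A will be completed only for adult participants in this study", while PRAS-ASD and SSP are given only to children and adolescents.

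**The concern.** Read literally, one listed objective has no analysis. The only factor-analysis sentence is attached to the other objective, and Cronbach's alpha is not a factor analysis.

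The between-scale sentence does not say which versions or which participants it covers. If each version were entered as a separate variable, the age rules could leave no participant with complete data.

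The item-level analysis also seems fragile. ARI has 55 items and is mandatory for only about 30 adults, so its item correlation matrix is singular. The number of factors found would depend heavily on an unstated retention rule. Because the study is meant to compare scales, an artefact of item count and sample size could be mistaken for a real difference between them.

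**Working it through.** **1. Sample per age group.** Section 9.1 gives six cohorts (two ABIQ strata by three age groups) of about 15. So 2 × 3 × 15 = 90, which reproduces the plan's figure, and 90 / 3 = 30 per age group. The sample size is not power-based, so there is no further figure to reproduce.

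**2. Complete cases for the repetitive-behaviour scales.** These are counted from Table 4 at 30 per age group, with no skips or dropouts. The lower figure uses mandatory forms only; the upper adds every optional form.

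| Set of scales | Mandatory only | All options given |
|---|---|---|
| CY-BOCS-ASD, MERS-R, RBS-R | 90 | 90 |
| These three + RBQ-2 + CRI-R | 30 + 30 = 60 | 90 |
| These three + RBQ-2A + ARI | 30 | 30 + 30 = 60 |
| All seven versions | 0 | 60 |

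**3. Pairs of scales.** Leaving out SB5, ADOS-2, CGI and RMET, Table 4 has 18 versions, hence 18 × 17 / 2 = 153 pairs. Six versions are mandatory at all ages, six only for children and adolescents, and six only for adults.

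- With mandatory forms only, 6 × 6 = 36 pairs share no participant. Of the 21 pairs among the seven repetitive-behaviour versions, 2 × 2 = 4 are affected.
- With options allowed, only BRIEF, SSP and PRAS-ASD (never adults) against BRIEF-A and HAM-A (adults only) can never overlap: 3 × 2 = 6 pairs. None involves a repetitive-behaviour scale.
- One matrix of all 18 versions has 0 complete cases under any option.

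**4. Singular item matrices.** The rank of a sample correlation matrix is at most n − 1.

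| Scale | Items | Minimum n | Maximum rank | Singular? |
|---|---|---|---|---|
| RBS-R | 43 | 90 | 89 | no |
| RBQ-2 | 20 | 60 | 59 | no |
| CRI-R | 62 | 60 | 59 | yes |
| ARI | 55 | 30 | 29 | yes |

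With every optional form given, CRI-R reaches n = 90 and ARI n = 60, so neither is forced to be singular (89 against 62; 59 against 55). Singularity rules out maximum-likelihood factoring. It does not rule out principal components, which Section 9.2.4 names, or minimum-residual factoring.

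**5. Number of factors.** The simulation used 600 replicates, normal items, equal loadings of 0.4 to 0.6 and factor correlations of 0, 0.3 or 0.5. Parallel analysis used the 95th percentile of 300 random samples. RBQ-2A is taken to have 20 items. All of these settings are assumptions. With one true factor, the eigenvalue-above-1 rule was right in 0% of samples and parallel analysis in 92–100%.

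| Scale (n) | Factors kept by eigenvalue > 1, one true | Parallel analysis right, two true | Parallel analysis right, four true |
|---|---|---|---|
| ARI (30) | 15.0–17.8 | 46–100% | 0–74% |
| CRI-R (60) | 16.7–21.6 | 88–100% | 7–100% |
| RBS-R (90) | 10.4–15.5 | 93–100% | 4–100% |
| RBQ-2 (60) | 4.6–7.4 | 37–100% | 0–83% |
| RBQ-2A (30) | 5.6–7.5 | 16–97% | 0–22% |

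At n = 60, which is possible if all adolescents also complete the adult forms, four-factor recovery is 6–100% for ARI and 1–83% for RBQ-2A.

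**6. Precision of a between-scale correlation.** The Fisher interval is tanh(atanh r ± 1.96/√(n − 3)). For r = 0.5, atanh r = 0.549.

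- n = 90: half-width 1.96/√87 = 0.210, interval 0.33–0.64.
- n = 60: half-width 1.96/√57 = 0.260, interval 0.28–0.67.
- n = 30: half-width 1.96/√27 = 0.377, interval 0.17–0.73.

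**The case for a change.** The strongest case for a change is that this is an omission and not just brevity: a listed objective has no stated method. The technical document cannot be seen, so it cannot be credited with supplying one. The choices left open also have consequences. Which versions enter decides whether the complete cases are 0 or 90. The retention rule decides whether a one-factor RBQ-2 is reported with one factor or with five to seven, and that result is not absurd enough to give itself away. Two sentences would settle both matters without new data.

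Much of this stands. Section 9 does leave the within-scale method unnamed and the between-scale set undefined. Six pairs outside the repetitive-behaviour scales cannot be estimated, and finer structure in the adult self-report scales will be poorly resolved if only about 30 adults complete them.

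The step to a defect does not stand. The plan does not call for one matrix of all versions, for maximum likelihood or for the eigenvalue rule; its wording leaves the method open. An analyst building the correlation table would see the empty cells, and maximum likelihood on a singular matrix would not run unnoticed.

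A tight prescription would also have costs. Confining correlations to one mandatory-version group per age band would discard adolescents' ARI and RBQ-2A and adults' RBQ-2 and CRI-R. The same-person comparison of caregiver report with self-report, which Section 8.1.1.3 makes possible, would go with them. Applied to the three common scales, it would replace n = 90 by 60 and 30. Marking every solution with four or more factors as unstable would prejudge RBS-R and CRI-R, where recovery reaches 100% under favourable loadings.

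**Conclusion.** No change to the plan is called for. This is a gap in detail that analysts can fill sensibly: item scores analysed by scale version in everyone who completed that version, an extraction that tolerates a singular matrix, a sound retention rule, and pairwise correlations with their n. The design supports this, with 30 to 90 complete cases for the workable sets of repetitive-behaviour scales. A two-factor split, the minimum suggested by the earlier factor analyses cited in Section 2.1, is recovered in 88–100% of simulated samples for CRI-R and RBS-R. It is less certain for RBQ-2 (37–100%), ARI (46–100%) and RBQ-2A (16–97%).

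The limits that remain come from sample size, and wording would not remove them. They bear on an objective framed as exploration, with p-values used descriptively.

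The conclusion assumes about 15 per cohort with no skips or dropouts, and Table 4 as the rule for who may receive each version. Section 8.1.1.18 restricts CSHQ to pediatric participants, whereas Table 4 allows it in adults. Under the restriction, the never-overlapping pairs become 4 × 2 = 8 instead of 6, still none among the repetitive-behaviour scales. The recovery figures depend on the assumed loadings and factor correlations. The conclusion does not depend on what the technical document contains, only on the fact that nothing in Section 9 commits analysts to a choice that would mislead.
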